11.5 Adherence to the Protocol

Except for an emergency situation in which proper care for the protection, safety, and well-being of the study patient requires alternative treatment, the study shall be conducted exactly as described in the approved protocol.

11.5.1 Emergency Modifications

Investigators may implement a deviation from, or a change of, the protocol to eliminate an immediate hazard(s) to trial subjects without prior IRB approval.

For any such emergency modification implemented, an IRB modification form must be completed within 5 business days of making the change, and the QAM must be notified within 24 hours of such change.

11.5.2 Other Protocol Deviations

All other deviations from the protocol must be reported to the assigned QAM using the appropriate form.

A protocol deviation is any unplanned variance from an IRB approved protocol that:

- Is generally noted or recognized after it occurs.
- Has no substantive effect on the risks to research participants.
- Has no substantive effect on the scientific integrity of the research plan or the value of the data collected.
- Did not result from willful or knowing misconduct on the part of the investigator(s).

A protocol deviation may be considered an instance of RNI(Reportable New Information) if it:

- Has harmed or increased the risk of harm to one or more research participants.
- Has damaged the scientific integrity of the data collected for the study.
- Results from willful or knowing misconduct on the part of the investigator(s).
- Demonstrates serious or continuing noncompliance with federal regulations, State laws, or University policies.

11.6 Investigator Obligations

The Principal Investigator is responsible for the conduct of the clinical trial at the site in accordance with Title 21 of the Code of Federal Regulations and/or the Declaration of Helsinki. The PI is responsible for personally overseeing the treatment of all study patients. The PI must assure that all study site personnel, including sub-investigators and other study staff members, adhere to the study protocol and all FDA/GCP/NCI regulations and guidelines regarding clinical trials both during and after study completion.

The Principal Investigator at each institution or site will be responsible for assuring that all the required data will be collected, entered onto the appropriate eCRFs, and submitted

within the study-specific timeframes. Periodically, monitoring visits may be conducted and the Principal Investigator will provide access to his/her original records to permit verification of proper entry of data. The study may also be subject to routine audits by the Audit Committee, as outlined in the DSMP.

Appendix I – International Working Group Response Criteria for AML

Definitions of response criteria are based primary on those given by Cheson et al.

Category	Definition
Complete remission (CR) ¹	Bone marrow blasts <5 percent; absence of blasts with Auer rods; absence of extramedullary disease; absolute neutrophil count >1.0 x 10 ⁹ /L (1000/μL); platelet count >100 x 10 ⁹ /L (100,000/μL); independence of red cell transfusions
CR with incomplete recovery (CRi) ²	All CR criteria except for residual neutropenia (<1.0 x 10 ⁹ /L (1000/μL)) or thrombocytopenia (<100 x 10 ⁹ /L (100,000/μL))
Morphologic leukemia-free state ³	Bone marrow blasts <5%; absence of blasts with Auer rods; absence of extramedullary disease; no hematologic recovery required.
Partial remission (PR)	All hematologic criteria of CR; decrease of bone marrow blast percentage to 5 to 25%; and decrease of pretreatment bone marrow blast percentage by at least 50%.
Cytogenic CR (CRc) ⁴	Reversion to a normal karyotype at the time of morphologic CR (or CRi) in cases with an abnormal karyotype at the time of diagnosis; based on the evaluation of 20 metaphase cells from bone marrow.
Molecular CR (CRm) ⁵	No standard definition; depends on molecular target.
Treatment failure	
Resistant disease (RD)	Failure to achieve CR, CRi or PR; only includes patients surviving ≥7 days following completion of initial treatment, with evidence of persistent leukemia by blood and/or bone marrow examination.
Death in aplasia	Deaths occurring ≥ 7 days following completion of initial treatment while cytopenic; with an aplastic or hypoplastic bone marrow obtained within 7 days of death, without evidence of persistent leukemia.
Death from indeterminate cause	Deaths occurring before completion of therapy, or <7 days following its completion; or deaths occurring ≥7 days following completion of initial therapy with no blasts in the blood, but no bone marrow examination available.
Relapse ⁶	Bone marrow blasts ≥ 5%; or reappearance of blasts in the blood; or development of extramedullary disease.

¹ All criteria need to be fulfilled; marrow evaluation should be based on a count of 200 nucleated cells in an aspirate with spicules; if ambiguous, consider repeat exam after 5 to 7 days; flow cytometric evaluation may help to distinguish between persistent leukemia and regenerating normal marrow; a marrow biopsy should be performed in cases of dry tap, or if no spicules are obtained; no minimum duration of response required.

² The criterion of CRi is of value in protocols using intensified induction or double induction strategies, in which hematologic recovery is not awaited, but intensive therapy will be continued. In such protocols, CR may even not be achieved in the course of the entire treatment plan. In these instances, the overall remission rate should include CR and CRi patients. Some patients may not achieve complete hematologic recovery upon longer observation times.

³ This category may be useful in the clinical development of novel agents within phase I clinical trials, in which a transient morphologic leukemia-free state may be achieved at the time of early response assessment.

⁴ Four studies showed that failure to convert to a normal karyotype at the time of CR predicts inferior outcome.

⁵ As an example, in CBF AML low-level PCR-positivity can be detected in patients even in long-term remission. Normalizing to 104 copies of ABL1 in accordance with standardized criteria, transcript levels below 10 to 12 copies appear to be predictive for long-term remission.

⁶ In cases with low blast percentages (5-10%), a repeat marrow should be performed to confirm relapse. Appearance of new dysplastic changes should be closely monitored for emerging relapse. In a patient who has been recently treated, dysplasia or a transient increase in blasts may reflect a chemotherapy effect and recovery of hematopoiesis. Cytogenetics should be tested to distinguish true relapse from therapy-related MDS/AML.

Appendix II – Revised IWG-MRT & ELN Response Criteria for MF

The criteria below are a revision of the International Working Group-Myeloproliferative Neoplasms Research and Treatment (IWG-MRT) criteria for treatment response in myelofibrosis (MF) and represents a collaborative effort by the IWG-MRT and the European LeukemiaNet to objectively assess the value of new drugs in inducing morphologic remission or improvement in MF-associated symptomatic burden (MF-SB).

Response Categories	Required Criteria ¹
CR (complete remission)	
 Bone marrow²: age-adjusted normocellularity; < 5% blasts; ≤ grade 1 MF³ Peripheral blood: hemoglobin ≥ 100 g/L and < ULN; neutrophil count ≥ 1 × 10⁹ and < ULN Platelet count ≥ 100 × 10⁹ and < ULN; < 2% immature myeloid cells⁴ Clinical: resolution of disease symptoms; spleen and liver not palpable; no evidence of EMH.
PR (partial remission)	
 Peripheral blood: hemoglobin ≥100 g/L and <UNL; neutrophil count ≥1 × 10⁹/L and <UNL; platelet count ≥100 × 10⁹/L and <UNL; <2% immature myeloid cells⁴ and Clinical: Resolution of disease symptoms; spleen and liver not palpable; no evidence of EMH or Bone marrow²: Age-adjusted normocellularity; <5% blasts; ≤grade 1 MF³, and peripheral blood: Hemoglobin ≥85 but <100 g/L and <UNL; neutrophil count ≥1 × 10⁹/L and <UNL; platelet count ≥50, but <100 × 10⁹/L and <UNL; <2% immature myeloid cells⁴ and Clinical: Resolution of disease symptoms; spleen and liver not palpable; no evidence of EMH
Clinical improvement (CI)	The achievement of anemia, spleen or symptoms response without progressive disease or increase in severity of anemia, thrombocytopenia, or neutropenia ⁵
Anemia response	
 Transfusion-independent patients: a ≥ 20 g/L increase in hemoglobin level⁶ Transfusion-dependent patients: becoming transfusion independent⁷
Spleen response ⁸	
 A baseline splenomegaly that is palpable at 5-10 CM, below the LCM, becomes not palpable⁹ 
OR
 
 A baseline splenomegaly that is palpable at > 10 cm, below the LCM, decreases by ≥ 50% 
A baseline splenomegaly that is palpable at <5 cm, below the LCM, is not eligible for spleen response

Symptoms response	A ≥ 50% reduction in the MPN-SAF TSS ¹⁰
Progressive disease ¹¹	
 Appearance of a new splenomegaly that is palpable at least 5 cm below the LCM or A ≥100% increase in palpable distance, below LCM, for baseline splenomegaly of 5-10 cm or A 50% increase in palpable distance, below LCM, for baseline splenomegaly of >10 cm or Leukemic transformation confirmed by a bone marrow blast count of ≥20% or A peripheral blood blast content of ≥20% associated with an absolute blast count of ≥1 × 10⁹/L that lasts for at least 2 weeks
Stable disease	Belonging to none of the above listed response categories.

Relapse	
 • No longer meeting criteria for at least CI after achieving CR, PR, or CI, or • Loss of anemia response persisting for at least 1 month or • Loss of spleen response persisting for at least 1 month
Recommendations for assessing treatment-induced cytogenetic and molecular changes	
Cytogenetic remission	
 • At least 10 metaphases must be analyzed for cytogenetic response evaluation and requires confirmation by repeat testing within 6 months window 
CR: eradication of a preexisting abnormality PR: ≥50% reduction in abnormal metaphases
 
Partial response applies only to patients with at least ten abnormal metaphases at baseline.

Molecular remission	
 • Molecular response evaluation must be analyzed in peripheral blood granulocytes and requires confirmation by repeat testing within 6 months window • CR: Eradication of a pre-existing abnormality • PR: ≥50% decrease in allele burden 
Partial response applies only to patients with at least 20% mutant allele burden at baseline.

Cytogenetic/molecular relapse	Re-emergence of a pre-existing cytogenetic or molecular abnormality that is confirmed by repeat testing.

EMH, extramedullary hematopoiesis (no evidence of EMH implies the absence of pathology- or imaging study-proven nonhepatosplenic EMH); LCM, left costal margin; UNL, upper normal limit.

¹ For all response categories, benefit must last for ≥12 wk to qualify as a response.

² Baseline and posttreatment bone marrow slides are to be interpreted at one sitting by a central review process. Cytogenetic and molecular responses are not required for CR assignment.

³ Grading of MF is according to the European classification. It is underscored that the consensus definition of a CR bone marrow is to be used only in those patients in which all other criteria are met, including resolution of leukoerythroblastosis. It should also be noted that it was a particularly difficult task for the working group to reach a consensus regarding what represents a complete histologic remission.

⁴ Immature myeloid cells constitute blasts + promyelocytes + myelocytes + metamyelocytes + nucleated red blood cells. In splenectomized patients, <5% immature myeloid cells is allowed.

⁵ See above for definitions of anemia response, spleen response, and progressive disease. Increase in severity of anemia constitutes the occurrence of new transfusion dependency or a ≥20 g/L decrease in hemoglobin level from pretreatment baseline that lasts for at least 12 weeks. Increase in severity of thrombocytopenia or neutropenia is defined as a 2-grade decline, from pretreatment baseline, in platelet count or absolute neutrophil count, according to the CTCAE v 4.0. In addition, assignment to CI requires a minimum platelet count of ≥25 000 × 10⁹/L and absolute neutrophil count of ≥0.5 × 10⁹/L.

⁶ Applicable only to patients with baseline hemoglobin of <100 g/L. In patients not meeting the strict criteria for transfusion dependency at the time of study enrollment (see as follows), but have received transfusions within the previous month, the pretransfusion hemoglobin level should be used as the baseline.

⁷ Transfusion dependency before study enrollment is defined as transfusions of at least 6 units of packed red blood cells (PRBC), in the 12 weeks prior to study enrollment, for a hemoglobin level of <85 g/L, in the absence of bleeding or treatment-induced anemia. In addition, the most recent transfusion episode must have occurred in the 28 days prior to study enrollment. Response in transfusion-dependent patients requires absence of any PRBC transfusions during any consecutive “rolling” 12-week interval during the treatment phase, capped by a hemoglobin level of ≥85 g/L.

⁸ In splenectomized patients, palpable hepatomegaly is substituted with the same measurement strategy.

⁹ For the purpose of this study, spleen or liver responses must be confirmed based on palpation/physical examination, or ultrasound if the body habitus is prohibitive, in keeping with standard care.

(Note: The original criteria mandates the use of imaging studies where a $\geq 35\%$ reduction in spleen volume, as assessed by MRI or CT, is required. Furthermore, a $\geq 35\%$ volume reduction in the spleen or liver, by MRI or CT, constitutes a response regardless of what is reported with physical examination.)

- ¹⁰ Symptoms are evaluated by the MPN-SAF TSS.¹⁷ The MPN-SAF TSS is assessed by the patients themselves and this includes fatigue, concentration, early satiety, inactivity, night sweats, itching, bone pain, abdominal discomfort, weight loss, and fevers. Scoring is from 0 (absent/as good as it can be) to 10 (worst imaginable/as bad as it can be) for each item. The MPN-SAF TSS is the summation of all the individual scores (0-100 scale). Symptoms response requires $\geq 50\%$ reduction in the MPN-SAF TSS.
- ¹¹ Progressive disease assignment for splenomegaly requires confirmation by MRI or computed tomography showing a $\geq 25\%$ increase in spleen volume from baseline. Baseline values for both physical examination and imaging studies refer to pretreatment baseline and not to posttreatment measurements.

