3.2 Inclusion Criteria – MF Patients

- 3.2.1 Patients must have a confirmed diagnosis (by blood or bone marrow) of myelofibrosis (MF), as defined by WHO criteria (see appendix II).
NOTE: If diagnosis was performed an outside facility, a copy of the report is sufficient for registration purposes; however, local pathology review at one of the main sites should still be obtained.
- 3.2.2 Patients must be intermediate I risk or beyond and meet the following:
- in need of treatment;
 - intolerant or refractory to ruxolitinib (or other investigational JAK-inhibitors) OR unlikely to benefit from ruxolitinib
 - ineligible or refusal to undergo stem cell transplantation.
- 3.2.3 Patients must be age ≥ 18 years.
- 3.2.4 Patients must have an ECOG status 0-2.
- 3.2.5 Patients must have adequate bone marrow and organ function within 2 weeks (14 days prior to registration, defined as:
- Direct bilirubin $\leq 1.5 \times \text{ULN}$
 - ALT/AST $\leq 2.5 \times \text{ULN}$
 - Creatinine $< 1.5 \times \text{ULN}$ or calculated creatinine clearance $> 30 \text{ ml/min}$
 - PT and PTT $\leq 1.5 \times \text{ULN}$
 - ANC $\geq 1000/\text{mm}^3$
 - Platelets $\geq 50,000/\text{mm}^3$
- Note: this must be achieved without transfusion.
- 3.2.6 Patients must have estimated life expectancy of 6 months or greater.
- 3.2.7 Female patients of child-bearing potential (FOCBP) must have a negative serum beta-HCG pregnancy test within 7 days prior to registration.
NOTE: See section 3.1 for definition of FOCBP.
- 3.2.8 Female patients must meet at least one of the following conditions:
- Must be post-menopausal for at least 1 year prior to registration (not of child-bearing potential as described above)
 - Must be surgically sterilized (as described above)
 - Willing to use an acceptable method of birth control (i.e. hormonal contraceptive, intra-uterine device, diaphragm with spermicide, condom with spermicide, or abstinence) for the duration of the study.
- 3.2.9 Male patients, even if surgically sterilized (i.e. status post-vasectomy) agrees to use an acceptable method for contraception during the entire study treatment period through 120 days after the last dose of alisertib. Likewise, female patients should agree to use acceptable method for contraception during the entire study treatment period through 90 days after the last dose of alisertib.
- 3.2.10 Patients must be able to understand and willing to sign a written informed consent.

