4.5.2 Permitted Concomitant Medications/Treatments

- Myeloid growth factors to treat patients with neutropenia according to the ASCO guidelines.
- Antiemetic agents may be administered at the discretion of the investigator but are not commonly required as a prophylactic agent.
- Antacids are permitted; however, they should be administered more than 2 hours before or 2 hours after administration of alisertib.
- Medications with potential CNS effects are not prohibited in this study, but it is recommended that their use be minimized to avoid confusion in the interpretation of CNS effects should they occur during the course of treatment with alisertib. Because of alisertib's structural and pharmacological similarity to the benzodiazepines, concomitant therapy with benzodiazepines is discouraged but not prohibited.
- Patients actively receiving hydroxyurea are eligible and may continue to receive hydroxyurea through cycle 1 of protocol treatment.
(Note: If the platelet count remains above 1 million after cycle 1, hydroxyurea can be used at the treating physician's discretion, if the platelets are $1000 \times 10^9/L$, or more, or if there are symptoms from thrombocytosis).
- Medications that can potentially reduce or increase effectiveness of alisertib, UGT 1A1/2/8 and moderate CYP 3A4, 2C9, 2C19, and 1A2 enzyme inducers or inhibitors, should be used with caution (see appendix III).
- All other medical conditions should be treated at the discretion of the investigator in accordance with local community standards of medical care.

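### Several response counts (AMKL platelets and ANC; MF hemoglobin, platelets and ANC) carry no transfusion- or growth-factor-free condition, so support can tip a patient who meets every other criterion into CR or PR

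*Combined protocol and SAP*

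**What the plan says.** Section 10.1.2 reports the proportion of evaluable patients with at least PR, with an exact 95% interval and no hypothesis. Categories come from the two appendices.

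- **AMKL (Appendix I).** CR needs ANC and platelet thresholds and "independence of red cell transfusions". PR takes over the hematologic criteria of CR and adds a fall in marrow blasts of at least half, to 5–25%. Platelet transfusion and growth factors are not mentioned.
- **MF (Appendix II).** CR and both PR routes set hemoglobin, ANC and platelet thresholds, such as "Peripheral blood: hemoglobin ≥100 g/L and <UNL", with no support condition in the rows or footnotes. They also require "resolution of disease symptoms; spleen and liver not palpable; no evidence of EMH". Footnote 1 adds: "For all response categories, benefit must last for ≥12 wk to qualify as a response".
- **MF anemia response (Appendix II).** The row reads "Transfusion-independent patients: a ≥ 20 g/L increase in hemoglobin level". Footnote 6 uses the pre-transfusion value as baseline for recently transfused patients. For transfusion-dependent patients footnote 7 is strict: "Response in transfusion-dependent patients requires absence of any PRBC transfusions during any consecutive" 12-week interval.
- **Support during the study.** Section 4.5.2 permits "Myeloid growth factors to treat patients with neutropenia according to the ASCO guidelines". Section 4.5 permits other necessary care, and transfusion is not on the prohibited list in 4.5.1.
- **Entry counts.** After the MF organ-function and count list, Section 3.2.5 states: "Note: this must be achieved without transfusion".

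**The concern.** Section 8.1.10 lists neutropenia, anemia and thrombocytopenia among effects seen in at least 10% of patients in earlier trials, so some transfusion and growth-factor use is foreseeable. A count raised by support says little about disease response. The plan recognizes this in places: red cells in Appendix I, the baseline hemoglobin and transfusion-dependent patients in Appendix II, and the MF entry counts. It leaves most on-treatment counts open.

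For the lower count thresholds, support can only add responders. At stake is the main efficacy figure of the study, in groups small enough that one patient matters.

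**Working it through.** **1. Which counts are protected**

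| Item | AMKL CR/PR | MF CR/PR | MF anemia response |
|---|---|---|---|
| Red cells / hemoglobin | Transfusion independence required | Threshold only | Baseline corrected (footnote 6); on-treatment value protected only in transfusion-dependent patients (footnote 7) |
| Platelets | >100 × 10⁹/L, no condition | ≥100, or 50 to <100 in the second PR route, no condition | – |
| ANC | >1.0 × 10⁹/L, no condition | ≥1 × 10⁹/L, no condition | – |
| Minimum duration | None | 12 weeks | 12 weeks |

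**2. AMKL PR.** Take a patient independent of red-cell transfusion, with blasts down from 40% to 15% and platelets 110 × 10⁹/L.

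- Blast fall: (40 − 15)/40 = 62.5%, at least 50%, and 15% lies within 5–25%. The marrow items are met.
- ANC 0.7: the CR count criteria fail, so PR fails. With persistent leukemia the patient is resistant disease, listed under treatment failure.
- ANC 1.1 on growth factor: every PR item is met.

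The same marrow changes category on one supported count. CR has an incomplete-recovery form (CRi) for patients whose counts lag; PR has none. AMKL entry (3.1.4) sets no ANC or platelet minimum, and Section 4.2 waives the new-cycle count requirements for cytopenia judged disease-related, so low counts at assessment are likely.

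**3. MF.** For CR or PR, a supported count matters only if the symptom, spleen, liver and other items are also met and the benefit lasts 12 weeks.

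For the anemia response, take a patient given 5 units in 12 weeks, with pre-transfusion hemoglobin 80 g/L and an on-treatment value of 100 g/L after transfusion. Five units is below the 6-unit definition of dependency, so the transfusion-free rule does not apply, and 100 − 80 = 20 g/L reaches the threshold. The value must still hold for 12 weeks, and the result is only clinical improvement (CI), which ranks below PR.

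**4. Size.** The plan's standard errors at a true rate of 10% come from √(p(1 − p)/n). One reclassified patient moves the rate by 1/n.

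| n | Standard error, computed | Standard error, plan | Shift from one patient |
|---|---|---|---|
| 24 | √(0.09/24) = 6.1% | 6% | 4.2 points |
| 12 | √(0.09/12) = 8.7% | 9% | 8.3 points |
| 6 | √(0.09/6) = 12.2% | 10–12% | 16.7 points |

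The plan's 18% for n = 18 does not reproduce (7.1%); that is a separate matter.

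With exact intervals, 2/24 = 8.3% (1.0–27.0) becomes 3/24 = 12.5% (2.7–32.4), and 0/6 = 0% (0–45.9) becomes 1/6 = 16.7% (0.4–64.1).

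**5. Range under an assumption.** The documents give no frequency of support-dependent counts. Suppose a share q of true non-responders meets everything else and reaches the counts only on support. The expected reported rate is then 0.10 + 0.90q: 11.8% for q = 2%, 14.5% for 5% and 19.0% for 10%.

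**The case against.** **Support alone.** A reader might infer that supportive care by itself can be scored as response. The documents do not support this. AMKL PR needs a real marrow change, and MF CR or PR needs the clinical items and 12 weeks of benefit. Support can only supply the count component.

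**Anemia response.** A reader might infer that this row inflates the response rate. It does not, because CI lies outside the at-least-PR proportion. Footnote 5 also denies CI when new transfusion dependency occurs. That guard is incomplete: the only definition of dependency, in footnote 7, describes the period before enrollment, needs 6 units and leaves out treatment-induced anemia.

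**Entry rule.** A reader might see a contradiction with Section 3.2.5. Its note follows a list with no hemoglobin criterion and does not mention growth factors, so the useful contrast is with platelets only.

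**Toxicity.** A reader might infer that the bias is known to grow with toxicity. That is plausible, but nothing in the documents measures it.

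**Importance.** The endpoint is secondary and descriptive, the criteria are adopted from published consensus, and the intervals in step 4 overlap almost entirely at n = 24. This stands. It makes the matter a modest one without removing the gap, and an interval for sampling error does not cover misclassification in one direction.

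**Conclusion.** The gap is real. AMKL platelets and ANC, and MF hemoglobin, platelets and ANC, can meet CR/PR thresholds on support. The consequence is confined to patients who satisfy every other criterion. It matters most for AMKL PR and is limited in MF by the 12-week rule. The MF anemia response has a related gap for patients short of transfusion dependency, which affects CI only.

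Each reclassified CR/PR patient is worth 4.2 points at n = 24, 8.3 at n = 12 and 16.7 at n = 6. The last matters because any disease split is allowed and the AMKL group may be very small. How many patients would be reclassified is unknown, and the rates in step 5 rest on assumed shares. This is an inexpensive improvement to a descriptive endpoint, not a threat to the primary safety objective.

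**What to change.** Add one scoring sentence to each appendix. These rules concern classification only and change no patient care.

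- **Platelets and ANC, both diseases.** A value meets a response threshold only if there was no platelet transfusion (for platelets) or myeloid growth factor (for ANC) in a prespecified preceding window. Seven days, with 14 days as a sensitivity analysis, is an assumption for the sponsor to confirm; the documents give no window.
- **MF hemoglobin.** A value counts for CR, PR or anemia response only with no red-cell transfusion over the 12-week interval already used in footnotes 1 and 7.
- **Supported values.** Score the item as not met until an unsupported value is available. Do not carry an earlier value forward: an unsupported ANC of 1.2 followed by 0.9 on growth factor would then be scored as met, although the current count fails even with support.
- **Data.** Record transfusion and growth-factor dates explicitly on the concomitant-medication form. The schedules in Sections 5.1 and 5.2 collect concomitant medications at most visits, but not at cycle 1 day 4, day 15 of cycles 2–6 or the end-of-study visit, so the form should cover the time since the last entry.
- **Reporting.** Also give the rate under the literal criteria, for comparison with other studies.

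The cost is a slightly lower reported rate and a minor departure from the published criteria. In MF, cycle 7 day 1 falls 6 × 21 = 126 days, or 18 weeks, after the start, so a red-cell transfusion after week 6 leaves the hemoglobin item unmet at that assessment. Sample size and visits do not change.

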10.1.2 Secondary Endpoint

To determine preliminary efficacy, response (defined as having at least PR in evaluable patients) will be reported as a proportion and 95% confidence interval using exact binomial methods. Given that this is a purely descriptive protocol, there is no set hypothesis regarding the response rate. Proportions for clinical response (defined as having at least PR or stable disease) will also be calculated. Please refer to appendices for detailed explanations of the clinical response criteria for each population.

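### In Appendix II the marrow route to MF partial remission caps both hemoglobin and platelets, so a patient with only one count reduced falls below PR while a patient with both reduced is PR

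*Combined protocol and SAP*

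**What the plan says.** The response table in Appendix II lists required criteria for each MF category.

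- **CR** needs the marrow, neutrophil, immature-cell and clinical items, with "hemoglobin ≥ 100 g/L and < ULN" and "Platelet count ≥ 100" × 10⁹/L.
- **PR, route without marrow**, repeats those blood limits, starting with "hemoglobin ≥100 g/L and <UNL", and drops the marrow item.
- **PR, marrow route**, keeps the marrow and clinical items and gives hemoglobin as "Hemoglobin ≥85 but <100 g/L and <UNL" and platelets as "platelet count ≥50, but <100 × 10⁹/L and <UNL". The two stand in the same semicolon-separated list as the neutrophil and immature-cell items.
- **Stable disease** is the residual category for anyone who fits no other. Clinical improvement covers an anemia, spleen or symptom response without progression or worsening cytopenia.

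Section 10.1.2 turns these categories into the secondary endpoint: "response (defined as having at least PR in evaluable patients) will be reported as a proportion", with an exact binomial 95% interval. The same section calls the protocol purely descriptive and sets no hypothesis on the response rate. It also plans a second proportion that counts PR or better together with stable disease.

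No footnote to Appendix II, and nothing in Sections 6.2 or 10.1.2, says how to classify a patient with one count in the reduced range and the other in the CR range.

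**The concern.** A response scale should not lower a patient's category because a blood count is better. The marrow route appears meant for patients whose marrow and clinical findings have remitted but whose blood counts have not fully recovered. As printed, it admits only those in whom both counts are incomplete. If one of the two has recovered, the patient fails the upper limit of the marrow route and still fails the lower limit of CR and of the other PR route.

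The mixed pattern can arise here. Section 3.2.5 admits MF patients with platelets from 50,000/mm³, Section 1.2 describes anemia in primary MF, and Sections 1.5.2 and 8.1.10 list anemia and thrombocytopenia among the effects of alisertib. A patient whose platelets stay at 60 × 10⁹/L can reach PR only by the marrow route, and that route closes once hemoglobin reaches 100 g/L.

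What is at stake is the proportion with PR or better and its interval. Without a stated rule, someone must choose between the literal text and a more sensible reading after seeing the patient's data.

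**Working it through.** The plan gives no figure on this point to reproduce. The check is to apply the printed rules to each combination of the two counts.

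**Held fixed:** marrow, neutrophil, immature-cell and clinical items all met, both counts below the upper limit of normal, and the 12-week duration in footnote 1 satisfied.

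**Rules from Appendix II**, with Hb in g/L and Plt in 10⁹/L:

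- CR: Hb ≥ 100 and Plt ≥ 100
- PR without marrow: Hb ≥ 100 and Plt ≥ 100
- PR by marrow: 85 ≤ Hb < 100 and 50 ≤ Plt < 100

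| Hb | Plt | CR or first PR route | Marrow PR route | Category as printed | Marrow route as lower bounds |
|---|---|---|---|---|---|
| 90 | 60 | fails both counts | met | PR | PR |
| 90 | 150 | fails on Hb | fails on Plt upper limit | below PR | PR |
| 105 | 60 | fails on Plt | fails on Hb upper limit | below PR | PR |
| 105 | 150 | met | not needed | CR | CR |

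Two of the four combinations at or above the reduced thresholds fall below PR. In each, one count is better than in the first row and the other is equal. The further limit at the upper normal value, printed after the limit of 100 in both bands, does not reopen either band.

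The last column reads the marrow route as Hb ≥ 85 and Plt ≥ 50, each below the upper limit of normal, with CR not met. Within the normal range, raising either count can then no longer lower the category.

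**Where the two middle rows go.** They become clinical improvement if its conditions are met, otherwise stable disease. Neither is a response under Section 10.1.2. A patient classed as clinical improvement is also not named in the second proportion, which mentions only PR or better and stable disease.

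**Size per patient.** One reclassified patient moves the proportion by 100/n points, where n is the number of evaluable MF patients. That number is not known in advance. The protocol allows all 24 subjects to be MF, and 18 and 12 are other sample sizes shown in Section 10.2:

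- n = 24: 100/24 = 4.2 points
- n = 18: 100/18 = 5.6 points
- n = 12: 100/12 = 8.3 points

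With assumed response counts and exact (Clopper-Pearson) 95% intervals:

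- n = 24: 2/24 = 8.3% (1.0% to 27.0%) becomes 3/24 = 12.5% (2.7% to 32.4%)
- n = 12: 1/12 = 8.3% (0.2% to 38.5%) becomes 2/12 = 16.7% (2.1% to 48.4%)

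**The case against.** The strongest reply is that these are adopted criteria. Appendix II presents the table as the revised IWG-MRT and ELN criteria, and Sections 2.2 and 6.2 commit the trial to IWG categories. Changing a named standard in one pilot costs comparability with other MF studies. Footnote 9 shows that the sponsor has already adapted the appendix for this study, but Appendix IV gives the reason as limited resources for CT and MRI, not a flaw in the criteria. This objection stands, and it is why the printed wording should remain the main analysis.

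The second reply is rarity. To be affected, a patient needs a marrow remission with at most grade 1 fibrosis, under 2% immature cells, resolved symptoms, impalpable spleen and liver, and no extramedullary disease. All of this must last 12 weeks, with exactly one count in the reduced band. The documents give no MF response rate for alisertib, and Section 1.6 says it has not been studied in MF. The evidence for mixed counts describes patients at entry or on drug, not patients in remission. This also stands: nothing in the documents shows how often the gap would matter.

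A reader might infer more than the text supports:

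- **That these patients have no category.** They do, because stable disease takes everyone left over.
- **That a sicker patient is preferred overall.** The comparison is of one lower count with everything else equal.
- **That the sponsor miscopied the criteria.** The source is not available here, and the literal gap is the same whether the wording is faithful or not.
- **That 4.2 to 8.3 points is an estimated bias.** It is 1/n for assumed denominators and would apply to any single reclassification.

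**Conclusion.** The gap is real on the printed text. A patient in marrow and clinical remission with one count in the reduced range and the other in the CR range is a non-responder, while a patient with both counts reduced is PR. Nothing elsewhere in the document resolves it.

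Its practical size is uncertain. The number of affected patients is unknown and may be zero, and each would shift the MF proportion by 1/n of evaluable patients. At n = 24 that shift is small beside an exact interval about 26 points wide at 2/24. Response is secondary and descriptive, so no power, error rate or decision rule is involved, and the primary safety objective is untouched.

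The conclusion rests on reading the semicolon-separated items as jointly required, as the column heading indicates, and on all other PR items being met. What justifies action is that the handling of mixed counts can be settled now at almost no cost instead of case by case after the data are seen.

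**What to change.** Keep the printed consensus criteria as the main analysis. Add a study-specific footnote to the marrow PR route in Appendix II, fixed before analysis, along these lines:

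> *In addition to the criteria as printed, the proportion with PR or better will be reported with the marrow route read as hemoglobin ≥ 85 g/L and platelets ≥ 50 × 10⁹/L, each below the upper limit of normal, with at least one below the CR limit. All other items are unchanged. The exact 95% interval and the number of patients whose category changes will be given.*

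Add a cross-reference in Section 10.1.2 so that the extra proportion is part of the planned analysis.

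The cost is one footnote and one extra reported proportion. That proportion departs from the consensus wording and must be labelled as doing so. No additional data are needed, because both counts and the marrow result are already collected. If no patient has mixed counts, the two proportions coincide and a single sentence says so.
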